7.8. Withdrawal Criteria

Due to the cRCT design, participants will receive the management toolkit or usual care whether they consent to the study or not. Participants can withdraw the use of the information collected at any time throughout the study. Consultees may also withdraw the patient if they feel they are experiencing anxiety or distress by continuing in the study.

All participants have the right to withdraw their information at any time, without having to give a reason. Investigator sites should try to ascertain the reason for withdrawal and document this reason on the withdrawal form and participant's medical notes.

The Investigator may discontinue a participant from the trial at any time if the Investigator considers it necessary for any reason including:

- Participant withdrawal of consent
- Significant protocol deviation or non-compliance
- Investigator's discretion that it is in the best interest of the participant to withdraw
- Termination of the study by the sponsor

Participants who withdraw from the trial will not be replaced.

7.9. End of Trial

The last contact for all participants in Work Package 5 will be at month 30. The end of the trial for regulatory purposes will be the locking of the database.

8. TRIAL INTERVENTION

8.1. Name and Description of Interventions

Management Toolkit:

The management toolkit is a guideline document that has been produced as part of the overall DIAMOND-Lewy programme grant. It is a document that offers practical advice to clinicians who are providing treatment and care to people with LBD (DLB and PDD).

8.2. Assessment of Compliance

Clinicians from participating services in the intervention arm will be asked to complete a questionnaire regarding use of the management toolkit. This will indicate:

- The level of completion and reasons
- Rates of compliance
- User experience

Consent will be implied through completion of the questionnaire. All clinicians in the intervention arm will be given the opportunity to complete the questionnaire at approximately 6 months following service randomisation and at the end of the study. This data will be used to answer key questions about the feasibility of use of the management toolkit in standard clinical care.

9. STATISTICAL CONSIDERATIONS

9.1. Analysis Population

Within the identified services all DLB cases (existing or new diagnosis) will be identified and will be eligible for inclusion, as long as they meet the inclusion criteria. Based on a previous work package where 70 DLB subjects were identified and recruited from a similar number of services over 18 months, it is anticipated work package 5 will recruit at least 60 subjects to enter the pilot study of the management toolkit (i.e. 30 in each arm).

In an earlier work package prevalence rates of PDD to be 10% were found of all PD subjects, therefore 8 services should be sufficient to allow a similar number of PDD subjects to be recruited (60 subjects, 30 in each arm) to enter the pilot study of the management toolkit.

9.2. Statistical Analyses

Hypothesis

For the definitive trial we hypothesise that DLB and for PDD subjects treated in services randomised to implementing the management toolkit will result in symptom improvement (reduced neuropsychiatric inventory score, lower unified Parkinson's disease rating scale score, greater improvement in CGIC global and symptom ratings), increased quality of life (DEMQOL and DEMQOL-proxy scales) and decreased carer stress (HADS, Zarit burden scale) at 6 months compared to baseline. In this pilot study, we will conduct an exploratory analysis where we will rehearse the analysis proposal for the full trial.

9.2.1. Analysis of the Outcome Measures

For the exploratory analysis, T-tests will be used to compare the means of two samples when data is normally distributed and a Wilcoxon Signed test will be used to compare the medians of two samples when data is

skewed. The association of a binary outcome with a categorical predictor with 2 or more levels will be tested using the Chi-square test. As there is a single management tool covering both dementia with Lewy bodies and Parkinson's disease dementia, then it will be appropriate to undertake exploratory analysis on the combined PDD and DLB subject group.

Information on the variability of continuous variables measuring the symptoms such as neuropsychiatric inventory score will be useful in power calculations for a larger study.

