4. TRIAL DESIGN

A pilot cluster randomised controlled trial (cRCT) design will be used to test the management toolkit. Participating services will be cluster randomised with half implementing the management toolkit (intervention arm) and half implementing usual clinical care (control arm). The study team will disseminate the management toolkit to the clinical teams in the intervention arm and provide appropriate training. Clinicians will use the toolkit as part of their clinical management of LBD patients according to their clinical judgement.

The study will be discussed and consent taken from the patient (or consultee) and the carer/informant for the additional study visits and for data to be collected for the study. For both arms of the study an additional visit will be arranged to conduct a baseline visit, 3 month and 6 month follow up visits.

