5. STUDY DURATION AND SETTING

This is a multi-centre study with at least 8 participating services. This study will be divided into two smaller parts: a) WP5A which will involve patients from memory assessment services, (Dementia with Lewy Bodies), and b) WP5B which will involve patients from neurology and geriatric services (Parkinson's Disease Dementia).

The total study duration will be 3 years. This will include a recruitment period of 24 months, a follow up period of 6 months and a final 6 months for data analyses, interpretation and dissemination of results. Submission of abstracts will continue beyond this period to target specific conferences and publications.

The management toolkit is a recommended guideline and will be used according to clinician judgement in the intervention arm. It could be used at a single visit only, or over multiple visits/patient contacts across several months. The management toolkit will be used as part of routine practice and will remain with sites after the end of the study. Additional study visits will be conducted at baseline, 3 months and

6 months, and clinicians in the intervention arm will be asked to complete a clinician toolkit use questionnaire.

Recruitment will be reviewed at the end of month 1 and regularly thereafter at study Trial Management Meetings. The end of month 30 will be the end of the study for all participants.

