7.3. Randomisation

Participating services will be randomised to administer either the management toolkit (intervention arm) or continue with usual care services (control arm). Randomisation will be done using computer generated randomisation at a service level, stratified by site (North East and East Anglia).

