9.2.2. Statistical Analyses

As the management tool covers both DLB and PDD it will be appropriate to undertake exploratory analysis on the combined PDD and DLB subject group. As the hypothesis concerns changes in symptom scores between baseline and 6 months we will use T-tests in an exploratory analysis to compare the means of two samples when data is normally distributed and a Wilcoxon Signed test will be used to compare the medians of two samples when data is skewed. The association of a binary outcome with a categorical predictor with 2 or more levels will be tested using the Chi-square test. Further analysis involving the data measured at baseline, 3 months and 6 months will be done by using a linear mixed regression model to test for between group and between time differences.

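### Services are randomised within region, but the t, Wilcoxon and chi-square tests treat patients as independent, so between-arm p-values are too small if patients within a service are correlated

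*Protocol*

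**What the plan says.** **Allocation.** Protocol section 4: "Participating services will be cluster randomised with half implementing the management toolkit (intervention arm) and half implementing usual clinical care (control arm"). Section 7.3: "Randomisation will be done using computer generated randomisation at a service level, stratified by site (North East and East Anglia").

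**Size.** Section 5: "This is a multi-centre study with at least 8 participating services". For the DLB part, section 9.1 says: "it is anticipated work package 5 will recruit at least 60 subjects to enter the pilot study of the management toolkit (i.e. 30 in each" (of the two arms). It plans a similar number, 60, for the PDD part. Section 9.3 justifies 30 per arm by a rule of thumb.

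**Tests.** Section 9.2.1: "T-tests will be used to compare the means of two samples when data is normally distributed", with a Wilcoxon test for skewed data. For binary outcomes: "The association of a binary outcome with a categorical predictor with 2 or more levels will be tested using the Chi-square test". Section 9.2.2 repeats these tests. Both sections allow DLB and PDD patients to be pooled. Section 9.2.2 adds, for the three visits, a "linear mixed regression model to test for between group and between time differences".

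**Status.** Section 9.2 calls the analysis exploratory and also a trial run of the definitive trial's analysis. Section 9.3 carries forward the variability of continuous scores to the power calculation for the larger study. Section 9 mentions neither an ICC nor a service effect.

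**The concern.** The unit of randomisation is the service, and the unit of the named tests is the patient. Patients in one service share clinicians, local practice and, in the toolkit arm, the same training and uptake. Pooling adds another source of similarity. DLB patients come from memory services and PDD patients from neurology and geriatric services, so any outcome difference between the diagnoses becomes a difference between services. A test that ignores this counts more independent information than there is.

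Two things are at stake. First, assessing the toolkit's impact on patients and carers is a stated objective (section 3.1), and p-values from these tests would overstate the evidence. Second, a pilot cluster trial is where the clustered analysis should be tried out and a first ICC obtained. The text as written asks for neither.

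**Working it through.** **The plan's own figures.** (60 + 60) patients × 2, counting carers, = 240, which matches the Trial Summary. The 30 per arm has no formula behind it to reproduce.

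**Inputs from the protocol.** 120 patients in the pooled analysis, 60 per arm. The number of services can be read in two ways:
- 8 in all (Trial Summary; at least 8 in section 5): m = 120/8 = 15 patients per service.
- 8 for each part (a possible reading of section 9.1), so 16: m = 120/16 = 7.5.

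**Assumptions, not in the protocol.** Two-sided 5%; ICC ρ = 0.01, 0.05, 0.10; equal service sizes; at first, no part of the between-service variance is regional.

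**Formulas.**
- Design effect: DE = 1 + (m − 1)ρ
- Reported SE / true SE = 1/√DE
- Real type I error = 2 × [1 − Φ(1.96/√DE)]
- Effective sample size = 120/DE

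Example with m = 15, ρ = 0.05: DE = 1 + 14 × 0.05 = 1.70; 1.96/√1.70 = 1.503; type I error = 13.3%.

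| Services × patients | ICC | DE | Reported/true SE | Type I error | Effective n |
|---|---|---|---|---|---|
| 8 × 15 | 0.01 | 1.14 | 0.94 | 6.6% | 105 |
| 8 × 15 | 0.05 | 1.70 | 0.77 | 13.3% | 71 |
| 8 × 15 | 0.10 | 2.40 | 0.65 | 20.6% | 50 |
| 16 × 7.5 | 0.01 | 1.065 | 0.97 | 5.8% | 113 |
| 16 × 7.5 | 0.05 | 1.325 | 0.87 | 8.9% | 91 |
| 16 × 7.5 | 0.10 | 1.65 | 0.78 | 12.7% | 73 |

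At ICC 0, DE = 1 and the rate is 5%.

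**Simulation.** With 20,000 null trials per case, 8 services of 15 gave 6.9% / 13.6% / 20.4% for the patient-level t-test. A t-test on service means (8 − 2 = 6 df) stayed between 4.9% and 5.2%.

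**Effect of the regional strata.** Randomisation balances the regions across arms, so a regional share s of the between-service variance drops out of the arm difference. With two services per arm in each region, DE becomes 1 + [m(1 − s) − 1]ρ. For m = 15 and s = 0.5:
- ρ = 0.05: 1 + 6.5 × 0.05 = 1.325, type I error about 9%.
- ρ = 0.10: 1 + 6.5 × 0.10 = 1.65, type I error about 13%.

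Simulation agrees. The inflation disappears only if nearly all the between-service variance is regional: m(1 − s) ≤ 1, that is s ≥ 14/15.

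**Chi-square test.** The direction is the same. I give no rates, because they depend on the prevalence and on whether the ICC is defined on the observed binary scale or a latent scale. The protocol gives neither.

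**The case against.** The strongest case on the other side has five parts.

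- **It is an exploratory pilot.** Its first objective is feasibility, no significance level or decision rule is stated, and section 9.3 concedes that the sample may be too small to test the hypothesis. This stands as a limit on the harm: the feasibility results do not depend on these tests. It does not remove the point, because section 9.2 makes this analysis the rehearsal for the full trial.
- **The mixed model may handle clustering.** A reader might infer that it covers repeated visits only and excludes service. The protocol does not support that. The random effects are simply not stated, and their structure is commonly left to a statistical analysis plan. Equally, a service effect in that model would not repair the t, Wilcoxon and chi-square tests.
- **Confidence intervals.** A reader might infer that the intervals for every clinical outcome will be wrong. Section 9 plans none, so the documents support only a statement about p-values and standard errors from the named tests.
- **The size is conditional.** The larger rates need an assumed ICC, 8 rather than 16 services, and no regional share of the variance. This stands, and the ranges above reflect it.
- **The two samples may be baseline and 6 months.** Section 9.2.2 can be read this way, since it refers to changes between those visits. Within one arm such tests would still ignore service, and they would not make the randomised comparison at all.

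**Conclusion.** The point holds in conditional form. The protocol allocates services within region but names patient-level tests, so between-arm p-values from those tests are too small when patients within a service are correlated beyond what region explains. The direction is clear and the size is not. For the t-test at an assumed two-sided 5%, and for ICC 0.01 to 0.10 with no regional share, type I error runs from about 6.6% to 21% with 8 services and from about 5.8% to 12.7% with 16. A half regional share with 8 services brings the rates at ICC 0.05 and 0.10 down to about 9% and 13%. Whether the mixed model includes service is an open question, not an error. That the fault will pass into the definitive trial is a risk and not a certainty, since that trial's protocol is not before us.

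**What to change.** Reword sections 9.2.1 and 9.2.2 so that every between-arm comparison accounts for service and for the regional stratum, by one of:

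- (a) a mixed model with random effects for service and for participant, region as a fixed effect, and a small-sample correction to the degrees of freedom (Kenward-Roger is one choice); or
- (b) an analysis of baseline-adjusted service-level summaries with region included, and degrees of freedom based on the number of services less the arm and stratum terms (8 − 2 − 1 = 5 with 8 services; 16 − 2 − 1 = 13 with 16).

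For binary outcomes, analyse service-level proportions or use a GEE or GLMM with a small-sample correction. State that service is a random effect in the model for the three visits. Report estimates with 95% confidence intervals, and the ICC with its interval, so that section 9.3 can carry both variability and ICC into the larger trial's power calculation.

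The cost is a change of wording. No new patients, visits or data are needed. Intervals will be wider, and an ICC from about 8 services will be imprecise and should be reported as such.

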9.2.2. Statistical Analyses

As the management tool covers both DLB and PDD it will be appropriate to undertake exploratory analysis on the combined PDD and DLB subject group. As the hypothesis concerns changes in symptom scores between baseline and 6 months we will use T-tests in an exploratory analysis to compare the means of two samples when data is normally distributed and a Wilcoxon Signed test will be used to compare the medians of two samples when data is skewed. The association of a binary outcome with a categorical predictor with 2 or more levels will be tested using the Chi-square test. Further analysis involving the data measured at baseline, 3 months and 6 months will be done by using a linear mixed regression model to test for between group and between time differences.

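### The test named for skewed outcomes is a paired test: it does not fit two independent arms, and used before-after it cannot show a toolkit effect

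*Protocol*

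**What the plan says.** Protocol 9.2.1 and 9.2.2 give the same pair of simple tests for continuous outcomes: t-tests, of unstated type, when data are normal, and a signed test when they are skewed. The wording in 9.2.2 is "a Wilcoxon Signed test will be used to compare the medians of two samples when data is skewed", and in 9.2.1 "a Wilcoxon Signed test will be used to compare the medians of two samples when data is" skewed. No rank-sum or other independent-samples rank test is named anywhere in the protocol.

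The two samples are not defined. Section 9.2.2 introduces the tests with "As the hypothesis concerns changes in symptom scores between baseline and 6 months we will use T-tests in an exploratory analysis", and the hypothesis in 9.2 expects improvement "at 6 months compared to baseline".

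The design is a comparison of two separate groups of patients. Section 4 assigns half the services to the toolkit and half to usual care, and 7.3 states "Randomisation will be done using computer generated randomisation at a service level".

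Two further statements bear on the point. Section 9.2.2 adds an analysis of the baseline, 3-month and 6-month data "by using a linear mixed regression model to test for between group and between time differences". Section 9.2 describes the pilot's purpose: "we will conduct an exploratory analysis where we will rehearse the analysis proposal for the full trial".

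**The concern.** The signed-rank test ranks the differences within pairs. Patients in toolkit services have no natural partner in usual-care services, so the test has nothing to work on between arms. Its natural use here is on each patient's own baseline and 6-month scores. That gives a before-after result in one arm and leaves the control arm out of the inference.

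An analyst who follows the sentence literally will therefore either be unable to run the test between arms or report within-arm p-values. The second outcome is the more harmful. A significant fall in a symptom score among toolkit patients could be read as benefit when regression to the mean, the effect of study visits or ordinary clinical change would produce the same fall under usual care. A sentence rehearsed in the pilot may also be carried into the definitive trial.

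**Working it through.** The protocol gives no alpha, power, effect size or SD for these tests, so there is no stated figure to reproduce. The check is first logical, then illustrative.

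**Reading A: the two samples are the arms.**
- The planned numbers are 30 per arm in each of WP5A and WP5B (9.1, 9.3), so 30 × 2 = 60 per arm when the DLB and PDD groups are combined.
- Patients in the two arms are different people in different services, so no pairs exist.
- With unequal arms the test cannot be computed. A trial run with arms of 58 and 55 returned an error.
- With equal arms, software will run it on whatever order the rows are in, so the p-value depends on an arbitrary pairing. In the simulation below this arbitrary pairing kept its error rate (5.3% with no common change and no effect). It was less powerful than the rank-sum test: 64% against 71%.

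**Reading B: the two samples are baseline and 6 months.**
The type of test then fits the data, but the hypothesis tested is no change over time within an arm. That hypothesis can be false when the toolkit does nothing.

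Illustrative simulation. All inputs are assumptions: 4,000 runs, 60 per arm, lognormal scores with log-scale SD 0.8 and baseline to 6-month correlation 0.6, two-sided 0.05, no clustering.

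| Common change (log scale) | Toolkit effect (log scale) | Signed-rank within toolkit arm | Rank-sum on change between arms |
|---|---|---|---|
| 0 | 0 | 5.1% | 5.3% |
| −0.25 | 0 | 66% | 6.0% |
| 0 | −0.4 | 97% | 71% |
| −0.25 | −0.4 | 100% | 60% |

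The second row carries the point. There is no toolkit effect, yet the within-arm test rejects in two runs out of three.

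A hand check on a different assumed case agrees. Take 60 patients, a natural change of 0.3 SD and a correlation of 0.6:
- SD of change = √[2(1 − 0.6)] = 0.894
- Standardised change = 0.3 / 0.894 = 0.335
- Noncentrality = 0.335 × √60 = 2.60
- Approximate rejection rate = Φ(2.60 − 1.96) = Φ(0.64) = 0.74, close to a simulated 0.70 for the signed-rank test (3,000 runs).

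**Would renaming the test be enough?**
No, because randomisation is by service. Assume 8 services, 4 per arm, with 120 / 8 = 15 patients each, and a single skewed score with no effect. An ordinary patient-level rank-sum test then gives:

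| ICC (assumed) | Design effect 1 + 14 × ICC | Rejection with no effect |
|---|---|---|
| 0 | 1.00 | 4.4% |
| 0.01 | 1.14 | 6.2% |
| 0.05 | 1.70 | 12.8% |
| 0.10 | 2.40 | 19.0% |

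**The case against.** A reader might infer that skewed outcomes get no valid between-arm result at all. The protocol does not support that. The mixed model in 9.2.2 tests between groups on all three time points and does not exclude skewed outcomes. Its text names neither a service effect nor a transformation, but that is detail a statistical analysis plan may supply.

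It can also be said that the signed test is not a mistake. The lead-in in 9.2.2 and the hypothesis in 9.2 both speak of change from baseline, and for that contrast a paired test is the right type. This stands as a reading of the sentence, but it does not rescue the test as evidence about the toolkit.

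The 66% and 70% figures are not error rates of this plan. They are the chance of detecting a real before-after change whose size is assumed, and they become false-positive rates only if the within-arm result is presented as a toolkit effect. Under Reading A they do not apply.

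Nor does the defect harm the planned use of the pilot for power calculations. The NPI is mentioned as an example of a score whose variability will be estimated, and an SD does not depend on which rank test is named. That the NPI will be skewed is a reasonable expectation, not something the protocol states.

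Finally, the analysis is exploratory, and 9.3 accepts that the numbers may be too small to test the hypothesis. That lowers the severity. It does not remove the point, because the protocol itself fixes a test and presents this analysis as a rehearsal.

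**Conclusion.** The concern holds for the simple test for skewed outcomes, and only there. On either reading, the test as written gives no proper comparison of the randomised arms: it lacks pairs, or it answers an uncontrolled before-after question. The unspecified t-tests in the same sentence share the uncertainty about which samples are meant. The logical part rests on the protocol text alone. The sizes rest on the assumed distributions, changes, correlations and ICCs shown above. Because a between-arm mixed model is also planned and the trial is an exploratory pilot, the severity is moderate.

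**What to change.** In both 9.2.1 and 9.2.2:

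1. State that the contrast is between arms, on 6-month change or on the 6-month score adjusted for baseline. This also settles which t-test is meant.
2. Delete the signed test and name an independent-samples method that respects randomisation by service. Either of these would serve:
   - the mixed model already planned, with a service random effect and baseline adjustment, and a transformed-scale sensitivity analysis for skewed scores;
   - a rank-sum test on service-level summaries, or one with a service-level permutation.
3. If within-arm changes are reported, label them descriptive.

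The cost in wording is small: the same short passage in two sections, with no change to data collection. The statistical cost comes from the number of services:
- With 8 services and two arms, a service-level comparison has about 8 − 2 = 6 degrees of freedom. The 95% multiplier rises from 1.96 to 2.45, a ratio of 1.25, so intervals are about 25% wider from this source alone.
- A 4 v 4 permutation has C(8,4) = 70 allocations, so the smallest two-sided p-value is 2/70 = 0.029. Section 7.3 stratifies by region. If each region had 4 services split 2 v 2 (an assumption, as the split is not given), there would be 6 × 6 = 36 allocations and a smallest p-value of 2/36 = 0.056. Estimates with intervals are therefore the better output for a pilot.
- A service-level bootstrap should not be relied on with about four services per arm.
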